- i. How will adverse events and unanticipated problems involving risks to subjects or others be reported, reviewed and managed? *Write here*
- ii. What provisions are in place for management of interim results? *Write here*
- iii. What will the multi-site process be for protocol modifications? *Write here*

13. **Statistical Considerations:** Describe the statistical analyses that support the study design.

Visit 1 Euglycemic Hyperinsulinemic Clamp: Sample Size: Prior work evaluating insulin sensitivity in youth with T1D is limited in consistency in reporting insulin-mediated glucose disposal. Thus, for sample size calculation, glucose infusion rate will be utilized as this calculation is more consistent across studies and can provide a good estimate of glucose disposal. A clinically meaningful difference would be at least 20% reduction in mean glucose disposal rate from lean to obese. In addition, we expect T1D lean young adults to have the highest mean glucose infusion rate, reflecting the anticipated response in T1D children not affected by hormonal changes of puberty (2). Therefore, we propose to compare the three means in a sequential manner: obese vs. lean adolescents with T1D, and lean adolescents with T1D vs. lean young adults with T1D, thus reducing the alpha level of 0.05 by $\frac{1}{2}$.

Using published literature (43,44), we will need 36 lean and 36 obese/overweight pubertal adolescents with T1D, to have 80% at alpha of 0.025, to detect a difference between group means of 13.6 (SD=3) and 11.5 mg/kg lean body mass/min (SD=3); and 36 lean young adults to detect a minimum percent increase in glucose infusion rate in the range of 15-18% from that of lean pubertal adolescents with T1D - for the respective sequential group comparisons. Of note, the literature suggests that the actual increase for the latter is around 30% ², therefore, we should be sufficiently powered.

An interim analysis will be conducted when we recruit 15 subjects in each group. If significant differences will be observed at that time, we will reconsider the sample size.

Data Analysis Approach: The departmental biostatistician [name], will guide [name] in analysis.

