- **Measures of Insulin Sensitivity:** Calculations will be conducted using methods used by Drs. [name] and [name] in previous work (41). Endogenous glucose production and fasting insulin levels will be used to calculate hepatic insulin resistance. Glycerol turnover will be utilized to assess adipose specific insulin sensitivity.

• Statistical Analysis: Descriptive statistics, such as mean, standard deviation, count, and percent, will be used to characterize the groups. Continuous variables will be compared among the three groups using the Kruskal-Wallis test or Analysis of Variance (ANOVA) for not Normal and Gaussian distributions respectively, followed by pair-wise group comparisons with either the Student's t-test or the Mann-Whitney U test, depending upon the normality in the distributional assumptions of the variables. Categorical variables will be compared with the Chi-square test or the Fisher's Exact test. Spearman Correlation will explore associations of the following assessments with measures of insulin suppression of hepatic glucose production and stimulation of peripheral glucose uptake.

- Glycemic control (HbA1c, fasting glucose)
- Additional measures of insulin sensitivity (endogenous glucose production, glycerol turnover, glucose oxidation, fat oxidation).

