Associations of these assessments with measures of insulin sensitivity will be explored for all groups. Unadjusted differences in the group means of primary and secondary outcomes of interest between lean and obese adolescent subjects, as well as between lean young adults and lean adolescent subjects, will be examined using the Student's t-test or the Mann-Whitney U test for variables with Gaussian and not normal distributions respectively. The impact of group, gender, sex hormones, pubertal stage, and growth factors on the outcome measures will also be explored using multivariable linear regression modeling. For the primary adjusted analysis, we will treat group as a categorical variable, and conduct two post-hoc pair-wise comparisons of means at alpha of 0.025. For the secondary adjusted analysis, we will also treat our three groups of subjects as an ordinal variable, whereby the lowest level will be given to the obese adolescents, followed by the lean adolescents, and then lean young adults. The latter approach will allow us to obtain a linear increase in the mean glucose disposal rate across the three groups, thus allowing us to use an alpha level of 0.05. The outcome variable will be normalized, if needed, using the natural log function.

Visit 2: Abdominal MRI: Sample Size: Based on mean hepatic lipid content in healthy overweight/obese and lean children ¹⁰, groups sizes of 36 lean and 36 obese adolescents will achieve >99% power at alpha of 0.05 to detect a difference between group means of 3.5% (SD=2) and 1.5% (SD=0.5). Even if a few subjects decline participation in this Aim, we will still have 90% power at alpha of 0.05 to detect the projected effect size using with a minimum of 12 subjects per group.

Data Analysis Approach:

The Proton Density Fat Fraction (PDFF) , a biomarker for hepatic steatosis, will be calculated from the liver images obtained liver PDFF parametric maps ⁹. A PDFF value above 5.5% is indicative of fatty liver ¹¹.

• Statistical Analysis: Descriptive statistics (mean, standard deviation, count, and percent) will be used to characterize the groups. Continuous variables will be compared between the lean and obese adolescents using either the Student's t-test or the Mann-Whitney U test. Categorical variables will be compared with the Chi-square test or the Fisher's Exact test. Associations of the following assessments with hepatic fat fraction will be explored through Spearman Correlation.

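### The interim look at 15 per group lets significant differences change the sample size but fixes no level, trigger or action; stopping or cutting on it would cost type I error or obese-vs-lean power

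*Combined protocol and SAP*

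**What the plan says.** The whole interim rule is two sentences under the Visit 1 sample size in Section I, item 13: "An interim analysis will be conducted when we recruit 15 subjects in each group", and then "If significant differences will be observed at that time, we will reconsider the sample size".

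The surrounding text implies that the endpoint is the glucose infusion rate and that the tests are the two pairwise comparisons, obese vs lean adolescents and lean adolescents vs lean young adults. On their order it says "we propose to compare the three means in a sequential manner", and then halves alpha from 0.05 because there are two comparisons.

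For young adults the design targets a "minimum percent increase in glucose infusion rate in the range of 15-18" per cent, and adds that "the literature suggests that the actual increase for the latter is around 30" per cent.

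The Statistical Analysis text of the same item describes an overall three-group test "followed by pair-wise group comparisons with either the Student's t-test or the Mann-Whitney U test". For the primary adjusted analysis it will "conduct two post-hoc pair-wise comparisons of means at alpha of 0.025". It does not mention the interim look again.

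**The concern.** The look is triggered by a comparative significance result, not by a variance check, and its result may change the sample size. Three things are missing:

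- **Level.** The 0.025 comes from splitting 0.05 over two comparisons, and all of it is used at the final analysis. Nothing is set aside for the look.
- **Trigger.** Nothing says whether one comparison or both must be significant. The sequential wording does not settle this, because halving alpha treats the two as parallel tests.
- **Action.** To reconsider could mean keep, raise, cut or stop.

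These actions have different consequences. Some do no harm, some inflate type I error, and one takes power away from the adiposity comparison, which is the study's stated purpose. A reader of the results could not tell which rule had been followed.

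**Working it through.** **Inputs from item 13.** Means 13.6 and 11.5 (difference 2.1), SD 3, 36 per group, look at 15 per group, 0.025 per comparison. Young-adult difference: 0.30 × 13.6 = 4.08 expected; 0.15 × 13.6 = 2.04 to 0.18 × 13.6 = 2.45 as the design minimum.

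**Assumed, because not stated.** Two-sided tests; young-adult SD 3 (results for SD 4 in brackets); 0.025 used at the look; the result is claimed if recruitment stops; unadjusted pooled t-tests.

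**1. The plan's own figure.** Noncentrality is 2.1 / (3 × √(2/36)) = 2.97. Power at two-sided 0.025 is 75.0% by the t distribution (76.7% by the normal approximation); one-sided it is 83.4%. The stated 80% is not reproduced either way. That is a separate matter; 75% is the no-look baseline here.

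**2. One comparison, no true difference.** The test statistics at the two looks correlate at √(15/36) = 0.645. The chance that either exceeds 2.241 in absolute value is 0.044, against 0.025 for one look.

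**3. Three groups, no true differences** (simulated, lean adolescents shared by both comparisons):

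| Action after a significant look | Error per comparison | Error for the two |
|---|---|---|
| n kept at 36 | 0.025 | 0.047 |
| n raised to 45-72, either triggers | 0.024-0.022 | not inflated |
| Stop, either triggers | 0.044 | 0.082 |
| Stop, both required | 0.028 | 0.049 |
| Cut to 24 and retest, either triggers | 0.029 | |
| Cut to 30 and retest, either triggers | 0.027 | |

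For stop on either, other readings give 0.043 and 0.086 (one-sided) and 0.065 and 0.120 (0.05 used at the look). If the overall ANOVA gates the pairs at an assumed 0.05, the figures are 0.034 and 0.062, against 0.020 and 0.035 with that gate and no look.

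**4. Young adults 30% higher.** At the look, noncentrality is 4.08 / (3 × √(2/15)) = 3.72, so that comparison is significant about 91% (78%) of the time. Effect on obese vs lean, with power at a difference of 2.1:

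| Trigger and action | Power | Type I error |
|---|---|---|
| No look | 75% | 0.025 |
| Either stops all groups | 37% (42%) | 0.027 (0.029) |
| Either cuts all groups to 24, retest | 56% | not materially inflated |
| Both required to stop | 77% (76%) | 0.041 (0.039) |
| Obese vs lean alone stops | 77% (77%) | 0.044 (0.044) |

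One-sided, stop on either gives 46% (49%) power against 83%.

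**5. Young adults 15-18% higher.** Their comparison is significant at the look 32-46% of the time. With stop on either, obese-vs-lean power is 61-55% and type I error 0.038-0.035.

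**6. Check of the remedies.** The O'Brien-Fleming constant for looks at 15 and 36 with 0.025 two-sided in total is 2.2447. At the look z = 2.2447 / 0.6455 = 3.48, so p < 0.0005; at the end p < 0.0248. Simulated type I error is 0.0249 per comparison and obese-vs-lean power about 74.9-75.0%. Re-estimating only the pooled SD (42 degrees of freedom, n = 36 × (s/3)²) gives 0.026 if n may only rise and 0.027 if it may also fall.

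**The case against.** The strongest reply is that the plan mentions neither stopping, nor claiming a result at 15 per group, nor tying adolescent recruitment to the young-adult result. Adiposity in adolescents is the title and first aim, so it would be odd for the young-adult comparison to end adolescent enrolment. Raising n would do good: at an assumed 54 per group, obese-vs-lean power is 91% when either comparison triggers and young adults are 30% higher. Mild cuts, or requiring both comparisons under no differences, move the error rate little. The study is non-randomised, cross-sectional and tests no treatment. The 0.025 is attached to an adjusted regression, not to the t-tests used here.

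Much of this stands, and it rules out stronger readings that a reader might infer:

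- That the plan as written has an error rate of 0.082 or a power of 37%. It does not; those figures need a stop that the text neither states nor excludes.
- That any reduction breaks the stated level. A cut to 30 gives about 0.027.
- That letting young adults stop all groups costs power with little type I inflation in general. That holds only near the 30% expectation; at 15-18% obese-vs-lean error is 0.038-0.035.
- That the unanswered prompt on managing interim results shows an omission. It belongs to the multi-site item, which is marked not applicable.

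The reply does not remove the gap. When differences are already significant, enrolling fewer is a natural meaning of reconsidering the sample size, and that is where the harm lies.

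**Conclusion.** The point holds as an under-specified rule with conditional consequences, and it should be fixed. That level, trigger and action are missing is certain from the text. The size of the harm depends on what is done:

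- **Keep or raise n:** no type I inflation.
- **Stop and claim, no true differences:** about 0.044 per comparison and 0.082 for the two on either trigger; about 0.028 per comparison if both are required.
- **Young-adult result allowed to stop all groups, at the plan's 30% expectation:** obese-vs-lean power falls by about half, from 75% to about 37% (42% with young-adult SD 4).
- **Adolescent numbers tied to obese vs lean alone, or to both comparisons, in that scenario:** stopping and claiming loses no power, but obese-vs-lean type I error is about 0.041-0.044.

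All figures rest on the assumed sidedness, young-adult SD and interim level, and on unadjusted t-tests. The adjusted regression cannot be simulated, because the documents give no covariate effects.

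**What to change.** Amend item 13 before the look, in two or three sentences.

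- **(a) Preferred.** State that the look cannot stop or reduce recruitment and that 36 per group are enrolled whatever it shows. This keeps 0.025 and needs no extra subjects; the cost is that early stopping is given up.
- **(b) If early stopping is wanted.** State that glucose infusion rate is tested at 15 and 36 per group with a two-look O'Brien-Fleming boundary, p < 0.0005 at the look and p < 0.0248 at the end for each comparison, and that adolescent numbers change only on obese vs lean. The cost is about 0.1 percentage point of power, and an early stop is unlikely (about 4% at a difference of 2.1). The restriction to obese vs lean matters: if the young-adult comparison could still stop all groups, obese-vs-lean power at the 30% expectation would be only about 46% (58% with young-adult SD 4), even with this boundary.

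If the look is instead used only to re-estimate the pooled within-group SD, with no group comparison, allow n to rise only. The cost is a possibly larger study.

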[figure not shown]
Visit 1: A hyperinsulinemic-euglycemic clamp will be conducted as a gold standard assessment of insulin sensitivity, with infusion of a stable

Hyperinsulinemic Euglycemic Clamp

glucose isotope in order to distinguish hepatic from peripheral insulin action.

Baseline glucose and glycerol turnover	Hepatic sensitivity to insulin (low dose infusion)	Peripheral sensitivity to insulin (high dose infusion)
Hyperinsulinemic euglycemic clamp		

Clamp studies will be carried out following methods utilized in Dr.

[name]'s lab ^{3,5}, as described briefly below. Participants will be admitted to the Hospital Research Unit (HRU) the evening prior to the clamp procedures for transition to IV insulin and stabilization of blood glucose with target of 90-100. On admission urine will be dipped for ketones, and if present, ketones will be managed as per routine clinical practice. If present, ketones will be monitored throughout treatment and the study will be delayed or cancelled pending resolution of ketosis. All participants will be advised to limit exercise in the 3 days prior to study to limit acute effects of recent exercise on insulin sensitivity. Females in the study who have reached menarche and have regular menses will be asked to keep a menstrual diary so that we can plan to study them during the follicular phase of the menstrual cycle (more insulin sensitive phase).

Baseline assessments will include liver function tests, lipids, sex steroids, IGF-1 (measure of growth hormone secretion), isoleucine, leucine, valine, and α -hydroxybutyrate.

- *Non-radioactive, Stable Isotope Tracer Infusions* will be employed to assess rates of glucose and lipid metabolism at the end of the 120 min baseline equilibration period and during the two stepped IV insulin infusion periods. From -120 to 0 min, 4.5 mg/kg of 6,6-²H₂-glucose (99% enriched; Cambridge Isotope Laboratories, Andover MA) will be followed by a continuous infusion at 0.03 mg/kg/min⁷. ²H₅-glycerol will be infused at 1.6 μ mol/kg followed by a constant infusion of 0.11 μ mol/kg/min⁷ to assess glycerol turnover. During the 120 min basal turnover period, a variable rate insulin infusion will be utilized to maintain plasma glucose between 90-110 mg/dL.

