- *Low Dose Insulin Infusion Period to Assess Hepatic Sensitivity to Insulin:* After obtaining baseline samples, subjects will receive a 10 mU/M² surface area /min infusion of insulin infusion for 120 minutes along with a variable 20% dextrose infusion with a goal of maintaining plasma glucose at 90-95 mg/dL.

- *High Dose Insulin Infusion Period to Assess Peripheral Sensitivity to Insulin:* The high dose insulin infusion of 80 mU/M² surface area/min will also continue for 120 minutes accompanied by a

variable 20% dextrose infusion ⁵. Plasma glucose will be monitored every 5 minutes during both insulin infusion periods by the YSI 2300 glucose analyzer to adjust dextrose infusion rates to maintain plasma glucose 90-95 mg/dL.

- *Metabolite Collection:* Samples for measurements of glucose and glycerol enrichment, as well as hormones and substrates, will be obtained every 5-10 minutes during the final 30 minutes of the baseline equilibration phase, as well as during the final 30 minutes of the low and high dose insulin infusion phases.

- *Measures of Oxidation:* Indirect calorimetry will be utilized at baseline and the end of each step of the clamp to evaluate rates of glucose and fat oxidation.

DEXA scan (Hologic, Boston, MA, USA): Total body fat and lean body mass will be assessed by dual energy x-ray absorptiometry (DEXA).

Visit 2: Adolescent participants (age 12-16). Young adults will not participate in this visit. Participants with transaminases >2.5 the upper limit of normal will undergo clinical evaluation to exclude liver disease (other than non-alcoholic steatosis) prior to proceeding with MRI.

Participants will present to the Magnetic Resonance Research Center (MRRC) for abdominal MRI. Using a 3Tesla Magnet (Siemens), we will assess intra-abdominal fat deposition and analyze the subcutaneous and visceral using methods our group has employed in the past ⁸.

We will quantitate the liver fat accumulation using the magnitude-based MRI of the liver to determine MRI-estimated Proton density fat fraction (PDFF) ⁹. The PDFF strongly correlates with hepatic steatosis as assessed by histopathology of liver biopsy. The 3T magnet will be used to scan participants and the gradient-recalled-echo technique will estimate liver PDFF ⁹.

5. Genetic Testing N/A

A. Describe

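### Endogenous glucose production is to be correlated with measures computed from it, so the usual test against zero correlation is not valid for those pairs

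*Combined protocol and SAP*

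**What the plan says.** All the relevant text is in Section I, item 13 (Statistical Considerations), under Visit 1, with the clamp procedures in item 4 (Research Plan).

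- The statistical analysis paragraph states: "Spearman Correlation will explore associations of the following assessments with measures of insulin suppression of hepatic glucose production and stimulation of peripheral glucose uptake". Two groups of assessments follow: glycemic control (HbA1c and fasting glucose), and "Additional measures of insulin sensitivity (endogenous glucose production, glycerol turnover, glucose oxidation, fat oxidation".
- The preceding paragraph, on measures of insulin sensitivity, states: "Endogenous glucose production and fasting insulin levels will be used to calculate hepatic insulin resistance".
- The text after the list widens the scope: "Associations of these assessments with measures of insulin sensitivity will be explored for all groups".
- Item 4 names the hepatic step of the clamp: "Low Dose Insulin Infusion Period to Assess Hepatic Sensitivity to Insulin". It also says how insulin is set before the clamp: "During the 120 min basal turnover period, a variable rate insulin infusion will be utilized to maintain plasma glucose between 90-110 mg/dL".

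The plan does not say whether the EGP to be correlated is the basal, low-dose-step or high-dose-step value. It writes out no formula for suppression or for the hepatic index, and refers the calculations to previous work. It gives no caution about pairs that share a component.

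**The concern.** Suppression of hepatic glucose production means the fall in EGP from baseline to a clamp step. Any measure of it, absolute or percentage, is computed from EGP. Correlating EGP with that measure puts the same measured value on both sides. The hepatic index has the same problem if the phrase about measures of insulin sensitivity is meant to include it.

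The default Spearman test asks whether the coefficient differs from zero. For a pair with a shared component, the coefficient that arises without any further biological link is generally not zero, so a small p-value does not show such a link. Because the plan calls EGP an additional measure of insulin sensitivity, a significant coefficient could be reported as agreement between two separate measures when part or all of it is arithmetic.

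**Working it through.** **Inputs from the documents.** EGP is in the list of correlates. Suppression is a target of the correlations. The hepatic index uses EGP and fasting insulin. There are 36 participants per group and 108 in total with the clamp. The plan states no expected coefficient and no variance for EGP or insulin, so there is no figure of its own to reproduce.

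**Assumptions.** Basal EGP (B), low-dose-step EGP (C) and fasting insulin (I) are log-normal. Percent suppression is 1 - C/B. The hepatic index is B x I. The within-person correlation of log B and log C is ρ, varied from 0 to 0.9.

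**Step 1: percent suppression.** The log-scale SD is s = sqrt(ln(1 + CV²)). A CV of 20% for B gives s_B = 0.198, and 40% for C gives s_C = 0.385. Percent suppression has the same rank order as ln B - ln C, whose SD is D = sqrt(s_B² + s_C² - 2ρ s_B s_C). Hence:

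- C against suppression: r = (ρ s_B - s_C)/D
- B against suppression: r = (s_B - ρ s_C)/D
- Spearman = (6/π) arcsin(r/2)

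| ρ | D | Spearman, low-dose-step EGP vs suppression | Spearman, basal EGP vs suppression |
|---|---|---|---|
| 0 | 0.433 | -0.88 | 0.44 |
| 0.3 | 0.377 | -0.85 | 0.21 |
| 0.5 | 0.334 | -0.85 | 0.02 |
| 0.7 | 0.284 | -0.86 | -0.24 |
| 0.9 | 0.224 | -0.92 | -0.64 |

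For example, at ρ = 0.5 the basal value is (0.198 - 0.5 x 0.385)/0.334 = 0.02. These are large-sample values. In simulation with n = 36, the average low-dose-step coefficient at ρ = 0.5 is -0.83, which gives the range of -0.83 to -0.92.

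If fractional suppression is instead drawn independently of basal EGP (assumed mean 60%, SD 10 to 15 percentage points, basal CV 20 to 30%), basal EGP against suppression is 0. Low-dose-step EGP against suppression is still -0.64 to -0.88.

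**Step 2: hepatic index.** With EGP and insulin independent, r = s_E / sqrt(s_E² + s_I²). For CVs of 20% and 50%, r = 0.198 / sqrt(0.198² + 0.472²) = 0.387, and Spearman is 0.37. Over EGP CVs of 15 to 30% and insulin CVs of 20 to 70%, Spearman runs from 0.22 to 0.82. Independence is not assured, because a variable-rate infusion sets insulin in the basal period. At CVs of 20% and 50%, a log-scale correlation of -0.4 between EGP and insulin brings Spearman to 0.02, and -0.6 brings it to -0.21.

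**Step 3: what the test would report.** The critical absolute coefficient at two-sided 0.05 is about 0.33 for n = 36 and 0.19 for n = 108. Every low-dose-step value above exceeds both. For the index, with independent components and EGP CV 20%, the simulated chance of p < 0.05 is:

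| Insulin CV | n = 36 | n = 108 |
|---|---|---|
| 30% | 0.93 | 1.00 |
| 50% | 0.60 | 0.98 |
| 70% | 0.36 | 0.87 |

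EGP and insulin are unrelated in this simulation, so the shared term alone produces these rates.

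**Step 4: pairs that can stay.** Peripheral uptake was taken as infusion rate plus residual EGP, with infusion rate mean 12 and SD 3, and residual EGP mean 0.8 and SD 0.2 to 1.0. EGP against uptake is then 0.06 to 0.25. The coupling is weak, and the top of that range needs a residual EGP SD larger than its mean. Item 4 has glucose and fat oxidation measured by indirect calorimetry, separately from the tracer and infusion measures.

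**The case against.** The best defence has four parts.

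- **Missing formulas.** The calculations are referred to earlier work, so the time point and formulas may be settled there. This limits what can be said about size and sign. It does not remove the shared term, because no definition of suppression of glucose production leaves out glucose production.
- **Not every pair is affected strongly.** This stands. A reader might infer that the planned correlations must be strong by arithmetic and carry no information. The documents do not support that. Basal EGP against percent suppression is near zero at ρ = 0.5 and negative above it, and it can be informative if judged against a suitable null. A coefficient of 0.44 at CVs of 20% and 40% needs basal and low-dose-step EGP to be independent within a person.
- **The index pairing is inferred.** This also stands in part. The named targets are suppression and peripheral uptake. The index enters only through the later general phrase.
- **The analysis is exploratory.** The plan attaches no alpha or decision rule to these correlations. That limits the harm but does not make the null right.

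A reader might also take glucose oxidation against peripheral uptake to be the same kind of artefact. It is not: oxidation is measured separately, and its being one fate of the glucose taken up is a biological relation.

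**Conclusion.** Wrong as written, and minor. The plan lists EGP as a correlate of a measure computed from EGP and, on a reasonable reading, of an index that contains it. For those pairs a test against zero is not valid.

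The clearest case is low-dose-step EGP against percent suppression, at about -0.83 to -0.92 under assumed CVs of 20% and 40%. For basal EGP even the sign is undetermined. For the index the range is about 0.2 to 0.8 if its components are independent, and lower or negative if they are inversely related. All these figures rest on assumed variances, log-normal distributions and assumed formulas, since the documents give none.

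Nothing here supports an inference that the lean versus obese or adolescent versus young adult comparisons are compromised. Neither those comparisons nor the sample size uses these coefficients.

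**What to change.** In the Visit 1 statistical analysis paragraph of item 13:

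1. Remove EGP as a correlate of the suppression measure and of the hepatic index. Alternatively, keep those pairs as descriptive, marked as sharing a component and reported without a p-value.
2. If the relation is of interest, regress low-dose-step EGP on basal EGP and group. The question is then put without a derived variable.
3. State which EGP value is used wherever it remains in the list, and write out the formulas for suppression and for the hepatic index.
4. Keep EGP against peripheral uptake, and keep the other listed correlates: HbA1c, fasting glucose, glycerol turnover, and glucose and fat oxidation. Do not re-express oxidation as a fraction of disposal for a correlation with disposal, because that would put disposal on both sides.

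The cost is a line or two of text. No data are lost, and at most one or two exploratory coefficients are dropped or relabelled.
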